## 2 STUDY OBJECTIVES AND RELATED ENDPOINTS

DS-group refers to the dose-stable group, i.e. participants receiving NR 1000 mg daily for 3 months. DE-group refers to the dose-escalation group, i.e. participants receiving NR 1000 mg in an escalating dose with 1000 mg from baseline to week 4, 2000 mg from week 4 to week 8 and 3000 mg from week 8 to week 12. PL-group refers to the placebo group.

Objective	Endpoint	
Primary	To compare the effect of orally administered nicotinamide riboside (NR), escalated to 1500 mg twice per day (3000 mg/day) in the dose-escalation group (DE-group) - versus stable dosing of 500 mg twice per day (1000 mg/day) in the dose-stable group (DS-group) on cerebral NAD-levels, at week 12.	Change in cerebral NAD/ATP- $\alpha$ ratio measured by $^{31}$ Phosphorus magnetic resonance spectroscopy ( $^{31}$ P-MRS) in the posterior brain (encompassing the occipital, parietooccipital and posterior parts of the temporal cortex).
Secondary	To assess the dose-response relationship between NR dose (1000 mg, 2000 mg, 3000 mg per day) and changes in cerebral NAD levels from baseline to weeks 4, 8 and 12.	Change in cerebral NAD/ATP- $\alpha$ ratio measured by $^{31}$ Phosphorus magnetic resonance spectroscopy ( $^{31}$ P-MRS) in the posterior brain (encompassing the occipital, parietooccipital and posterior parts of the temporal cortex).
	To compare the effectiveness of orally administered nicotinamide riboside (NR) 1500 mg twice per day versus 500 mg twice per day in augmenting the NAD-metabolome in the central nervous system (CNS) at week 12.	Change in the cerebrospinal fluid (CSF) levels of NAD or other metabolites of the NAD metabolome*, measured by LC-MS.
Exploratory	Neuroimaging	
	To compare the effect of orally administered NR in the DE-group versus DS-group on the NR related metabolic pattern (NRRP) expression at week 12.	Change in NRRP expression, measured by FDG-PET.
	To assess the dose-response relationship between NR dose (1000 mg, 2000 mg, 3000 mg per day) and changes in NRRP expression from baseline to weeks 4, 8 and 12.	Change in NRRP expression, measured by FDG-PET.
	To compare the effect of orally administered NR DE-group versus DS-group on the PD-related pattern (PDRP) expression at week 12.	Change in PDRP expression, measured by FDG-PET.

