#### 1.3.2 Secondary Objectives

The secondary objectives of this study are to:

- Assess the dose-response relationship between NR dose (1000 mg, 2000 mg, 3000 mg per day) and changes in cerebral NAD levels from baseline to weeks 4, 8 and 12.

- Compare the effectiveness of orally administered nicotinamide riboside (NR) 1500 mg twice per day versus 500 mg twice per day in augmenting the NAD-metabolome in the central nervous system (CNS) at week 12.

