#### 5.1.2 Primary Inferential Analysis

The *primary analysis* of the *primary endpoint* will be performed using analysis of covariance (ANCOVA) between the dose stable (DS-group) and dose escalation group (DE-group), i.e. the regression of NAD levels measured by P-MRS at week 12 depending on randomization group and adjusted for P-MRS at baseline. No additional adjustments/covariates will be used. As this is the single primary outcome, alpha will be set at 0.05. No correction for multiple testing will be performed.

The formula for this calculation in R is:

```
lm_object = lm(NAD_at_V4 ~ Group + NAD_at_V1)
```

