### 5.1.7 Secondary Analyses of the Primary Endpoint

The *secondary analyses* of the *primary endpoint* will be:

1. Analysis of covariance (ANCOVA) between the dose stable (DS-group) and placebo group (PL-group), i.e. the regression of NAD levels measured by P-MRS at week 12 depending on randomization group and adjusted for P-MRS at baseline. No additional adjustments/covariates will be used. No correction for multiple testing will be performed.

The above-mentioned analysis will be performed in the same manner as the primary analysis for the primary endpoint.

2. Comparison of change over time from baseline to week 4, week 8 and week 12, between the DE-group, DS-group and the PL-group. This will be assessed using a linear mixed model (LME), i.e. NAD (P-MRS) at weeks 4, 8 and 12 depending on randomization group, time and their interaction adjusted for random individual intercept. The above-mentioned analysis will be performed using a linear mixed model (LME) comparing NAD level as a function of group with time and the interaction between group and time as independent variables. Individual subjects will be random effects.

The following formula will be used in R format:

```
NAD_level ~ Group + Visit + Group * Visit + (1 | Subject)
```

Visit will be treated as a numeric variable if there is no plateau effect. If there is a plateau effect in the data, visit will be treated as a factor.

The primary effect estimate will be the B-coefficient with confidence intervals and Cohen's d. Cohen's d will be calculated as the difference in the means between two groups and divided by the pooled standard deviation.

The dose stable group will be set as the reference to which the dose escalation and placebo groups will be compared.

No additional covariates will be included in the LME model.

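### The SAP's mixed model for dose-response leaves the DE-DS difference free at baseline and week 4, when both arms have had the same regimen: valid, but inefficient, and without a trend per 1000 mg

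*SAP*

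**What the plan says.** SAP 1.3.2 sets the objective, to be assessed at each of the three follow-up visits: "Assess the dose-response relationship between NR dose (1000 mg, 2000 mg, 3000 mg per day) and changes in cerebral NAD levels". Protocol section 2 gives the DE regimen as "1000 mg from baseline to week 4, 2000 mg from week 4 to week 8 and 3000 mg from week 8 to week 12"; DS stays on 1000 mg throughout. Protocol 5.2 shows the same capsule make-up in both arms for the first four weeks.

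SAP 5.1.7 specifies a mixed model "comparing NAD level as a function of group with time and the interaction between group and time as independent variables", with a random intercept per subject. "The dose stable group will be set as the reference to which the dose escalation and placebo groups will be compared", and "No additional covariates will be included in the LME model". On coding, "Visit will be treated as a numeric variable if there is no plateau effect"; otherwise it is a factor. The primary week-12 ANCOVA (SAP 5.1.2) contains arm and baseline only: "No additional adjustments/covariates will be used". SAP 5.3 carries the same models over to exploratory outcomes measured at all four visits. Dose level appears elsewhere only in the descriptive adverse-event tables (SAP 6.1.1).

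I take the mixed model to use all four visits. One sentence in 5.1.7 names weeks 4, 8 and 12 alone, so the SAP should say which is meant.

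**The concern.** No specified model contains dose, and none uses the fact that DE and DS are interchangeable until the first step-up. Under randomisation and blinding the expected DE-DS difference is zero at V1 and again at V2. The planned model spends parameters on both differences. A chance imbalance at V1 then passes straight into the week-12 interaction, and the V2 scan does nothing to correct it.

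This matters because Protocol 1.3.2 and 1.4 describe wide variation between people in cerebral NAD response to 1000 mg. The week-4 scan measures each person's response at that dose before the arms diverge. At stake is the precision of the dose-response answer from scans that are collected anyway.

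The model also yields no effect per 1000 mg. With Visit numeric and a response linear in dose, the DE slope is one dose step per visit. The DS doses 0, 1, 1, 1 have a least-squares slope of (-0.5 + 0.5 + 1.5)/5 = 0.3. The reported DE-DS slope is then 0.7 of the effect per 1000 mg.

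**Working it through.** The plan states no precision for this contrast, so there is no figure of its own to reproduce.

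**Inputs.** DE 40, DS 20 and PL 20 (SAP 1.2). The SD of change is not stated. Protocol 1.3.2 gives P = 0.016 for the paired test in the earlier 1000 mg trial, and SAP 5.5 gives an increase by a factor of 1.27. With n = 15 assumed, t on 14 df is 2.74 and SD = 0.27 x √15 / 2.74 = 0.38 of baseline. Two further quantities are assumed: f, the share of the variance of change that is true response variation, and ρ, the correlation between two scans apart from response. I use ρ = 0.3, 0.5 and 0.7, and the same mean and spread of response at every dose.

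**Set-up.** Let V be the variance of change. Noise per visit is w = (1-f)V/2, response variance is r = fV, and stable between-person variance is a = wρ/(1-ρ).

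**Planned contrast.** With Visit as a factor, the DE x V4 term is a difference in mean change. Its variance is V(1/40 + 1/20) = 0.075V = 0.075 x 0.1444 = 0.0108, so the SE is 0.104.

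**Constrained contrast (DE = DS at V1 and V2).** The variance is 0.075 x Var(Y4 | Y1, Y2).

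- *f = 0.* The ratio planned/constrained is 2(1-ρ) / [1 - 2ρ²/(1+ρ)]. At ρ = 0.5 this is 1.0/0.667 = 1.50.
- *f = 0.5, ρ = 0.5, in units of V.* w = 0.25, r = 0.5, a = 0.25. So Var(Y1) = 0.5, Var(Y2) = Var(Y4) = 1, cov(Y1,Y2) = cov(Y1,Y4) = 0.25 and cov(Y2,Y4) = 0.75. The regression weights on Y1 and Y2 are 0.143 and 0.714. The explained part is 0.25 x 0.143 + 0.75 x 0.714 = 0.571, which leaves 0.429. The ratio is 1/0.429 = 2.33.

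Planned variance divided by the alternative's variance, at ρ = 0.3 / 0.5 / 0.7:

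| f | common baseline only | equal at V1 and V2 | added by V2 |
|---|---|---|---|
| 0 | 1.54 / 1.33 / 1.18 | 1.62 / 1.50 / 1.42 | 1.06 / 1.12 / 1.20 |
| 0.25 | 1.36 / 1.23 / 1.13 | 1.79 / 1.73 / 1.69 | 1.32 / 1.41 / 1.50 |
| 0.5 | 1.21 / 1.14 / 1.08 | 2.36 / 2.33 / 2.31 | 1.94 / 2.04 / 2.14 |

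V cancels, so these ratios do not depend on the backed-out SD. The middle column is the gain over the planned interaction. The last column is the gain beyond baseline adjustment, and so approximately what adding V2 to the week-12 ANCOVA would bring.

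**Check on a current-dose model.** Visit plus categorical current dose, with placebo as 0 mg, assumes that the 1000 mg effect is constant from week 4 to week 12. Suppose there is no dose effect, but the 1000 mg response grows from 0.27 at week 4 to 0.405 (+50%) or 0.54 (doubled) at week 12 in both NR arms. At f = 0 and ρ = 0.5 the model reports a spurious 3000 v 1000 mg difference of 0.050 or 0.100 with SE 0.073. The rejection rate is Φ(-1.96 + bias/SE) + Φ(-1.96 - bias/SE), which is about 10% or 28%. Across ρ = 0.3-0.7 it is 10-11% and 26-29%, and it is higher at larger f. The constrained arm contrast stays at 5%, because DE and DS still share the same mean at every visit.

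**The case against.** The strongest reply is that the plan already delivers most of what the objective needs. With Visit as a factor and DS as reference, the DE x V3 and DE x V4 terms are the 2000 v 1000 mg and 3000 v 1000 mg contrasts. This stands. A reader might infer that dose-response goes unanswered because no model has a dose term; the documents do not support that. Only the trend per 1000 mg is missing, along with labelling of the contrasts by dose.

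A second reply is that the week-4 equality is a small part of the gain. At f = 0 that is right: V2 adds a factor of 1.06-1.20, and the rest is baseline adjustment, which the primary ANCOVA has. V2 becomes important only if response truly differs between people. Protocol 1.3.2 offers that as a possible explanation and does not separate it from scan noise.

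A third stronger reading is that a visit-plus-current-dose model should replace the arm-based one. Under a random-intercept covariance it cuts the variance of the 3000 v 1000 mg contrast by 47-54% (ρ = 0.3-0.9). But in DE dose and duration rise together, so it gives up the protection of randomisation. The plateau within 1-2 weeks cited in Protocol 10.3 lends support, but the protocol does not say that it was measured in the brain.

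Finally, V2 equality is not guaranteed. Appendix B of the protocol allows imaging up to 72 hours after the examination, and the next supply is dispensed at V2. A late scan in DE could follow the step-up.

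**Conclusion.** The point holds as one of efficiency, not validity. The planned Group x Visit analysis is unbiased for the arm contrasts but leaves the DE-DS difference free at two visits where it is known to be zero. Removing that freedom divides the week-12 variance by about 1.4-1.6 (f = 0), 1.7-1.8 (f = 0.25) or 2.3-2.4 (f = 0.5). The SE falls from 0.104 to about 0.082-0.087, 0.078-0.080 or 0.068 respectively. These figures rest on assumed f and ρ, complete data, and a spread of response that does not grow with dose. The SEs also rest on the SD of 0.38.

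Nothing here shows that the primary week-12 ANCOVA is invalid or needs changing. It is a proper randomised comparison, and the V2-adjusted version is meant only to support it.

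**What to change.** In SAP 5.1.7:

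- Fit the mixed model with Visit as a factor, all arms equal at V1, and DE equal to DS at V2. The mean then has four visit terms, PL terms at V2-V4 and DE terms at V3-V4: 9 parameters instead of 12.
- Use a covariance not limited to a random intercept, such as unstructured across the four visits.
- Report DE-DS at week 8 as 2000 v 1000 mg and at week 12 as 3000 v 1000 mg.
- Add a supportive ANCOVA, `NAD_at_V4 ~ Group + NAD_at_V1 + NAD_at_V2`. V2 is post-randomisation, but treatment is identical up to then, so adjusting for it removes no treatment effect.
- If a trend per 1000 mg is wanted, add a visit-plus-current-dose model labelled exploratory, beside the arm-based one. State that it assumes no duration or carry-over effect and is biased if the 1000 mg response keeps growing after week 4.
- Flag V2 scans taken after the step-up and repeat the analyses without them.

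The cost is SAP wording and one or two extra fits, with no new data. Participants without a V2 scan drop out of the supportive ANCOVA. The change should be made before treatment codes are opened, since added later it would be post hoc.

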### 1.3.2 Phase I evidence for NR-therapy in PD

Two phase I studies of NR in PD have been completed, the **NADPARK** study and the **NR-SAFE** study. These are described briefly below.

**I. The NADPARK study** (ClinicalTrials.gov: NCT03816020) is a phase I randomized, double blinded trial, aiming to assess the tolerability, cerebral bioavailability and molecular effects of NR therapy in PD. A total of 30 individuals with newly diagnosed, drug-naïve PD were randomized to NR 500 mg x2/day or placebo for 30 days. The study showed promising results, which were published in 2022 and are briefly summarized below:

**1) NR is well-tolerated:** NR 1000 mg per day has excellent compliance, tolerability and no signs of toxicity or adverse effects in PD.

[figure not shown]
**2) NR achieves brain penetration:** *In vivo* measurement of cerebral NAD levels using phosphorus magnetic resonance spectroscopy (31P-MRS) of the brain showed a highly significant (paired t-test: P = 0.016) **increase in cerebral NAD levels** in the NR group, while no change was observed in the placebo group (**Fig 1A-C**). Cerebral penetration was further validated by detecting the metabolite Me-2-PY in the CSF of participants receiving NR, but not placebo (**Fig 1G**). While a significant NR-induced increase in cerebral NAD levels was detected at the group level, this effect was not uniform at the individual level. The magnitude of the cerebral NAD-increase showed high interindividual variation (**Fig 1C**). Moreover, three participants showed no evidence of cerebral NAD response, despite a clear peripheral metabolic response, confirming treatment compliance and an impact on the NAD metabolome, in CSF, blood, and muscle. Thus, the variable cerebral NAD response observed by P-MRS may reflect interindividual variability in cerebral penetration and/or cerebral NAD metabolism.

**3) NR is associated with clinical improvement of PD:** NR was associated with a significant decrease in the total MDS-UPDRS (I-III) score between visits (mean decrease: 2.33 ± 2.35; paired t-test: p = 0.017).

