## 10 STATISTICAL METHODS AND DATA ANALYSIS

### 10.1 Determination of Sample Size

Our primary null hypothesis ( $H_0$ ) is that the NR-induced increases in cerebral NAD levels (measured by 31P-MRS) are not dose-responsive. The alternative hypothesis ( $H_A$ ) is that this measure is dose responsive. In the NADPARK study, all three measures showed a highly significant increase in the group receiving 1000 mg NR ( $n = 15$ ) compared to the placebo group ( $n = 15$ ). In the NADPARK study, treatment with 1000mg of NR led to an increase in cerebral NAD-levels by a factor of 1.27 from baseline in the treatment group, whereas the change in the placebo group was negligible at -0.43%. Under the  $H_A$ , we assume that cerebral NAD levels will increase in a linear fashion in the 2000 mg NR and 3000 mg NR groups, respectively. Based on these assumptions and given a type I error rate of 5% ( $\alpha = 0.05$ ) and a type II error rate of 10% ( $\beta = 0.1$ , power = 90%), we estimated that a sample size of 30 individuals will be required in the dose escalation group. Accounting for drop-out and statistical safety margin, we estimate that the study requires 40 subjects in this group.

For the secondary and exploratory outcomes, we assume that the metabolomic, transcriptomic and inflammatory cytokine analyses will have sufficient power, since they produced very large effect sizes and highly significant results in the NADPARK study with 15 individuals per group. Since no pilot data exists for the proteomic and epigenomic analyses, these will be exploratory in nature. However, in our previous experience, a sample size of 20 per group should be sufficient to detect treatment-induced differences of biological relevance.

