## 1 Introduction

### 1.1 Background and Rationale

Increasing evidence supports that boosting cellular levels of nicotinamide adenine dinucleotide (NAD) confers neuroprotective effects in both healthy aging and neurodegeneration. Increasing NAD via supplementation of precursors have shown beneficial effects on life- and health span in multiple model systems, and evidence of neuroprotection in models of neurodegeneration and other age-related diseases. NAD can be replenished via supplementation of nicotinamide riboside (NR), a vitamin B3 analog and biosynthetic precursor of NAD. NR has undergone extensive preclinical testing and is well tolerated by adult humans, showing no evidence of toxicity with doses up to 2000 and 3000 mg daily. In two recent trials of NR in PD, increase in cerebral and whole blood NAD and an association with clinical improvement was seen. This response was heterogeneous, and it is unknown if this was due to inadequate dosing. We are therefore conducting the N-DOSE trial, investigating the dose-response and effect of an increasing dose of NR dose from 1000mg to 3000mg.

We refer the reader to the N-DOSE protocol for a more detailed description.

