#### 2.3.2 Confidence Intervals and p-values

All calculated p-values will be two-sided and compared to a 5% significance level. If a p-value is less than 0.05, the corresponding treatment group difference will be denoted as statistically significant. All efficacy estimates will be presented with two-sided 95% confidence intervals. As there is only one primary null hypothesis to be tested in this trial, there will be no adjustments for multiplicity.

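### The mixed model for the NAD time course (SAP 5.1.7) is not robust to the heterogeneous NR responses the documents report: its week-12 DE–DS false-positive rate could be near 22% or near 5%, depending on quantities the documents do not give

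*SAP*

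**What the plan says.** SAP 5.1.7 gives the second secondary analysis of the primary endpoint as "NAD_level ~ Group + Visit + Group * Visit + (1 | Subject". In words, NAD is modelled "depending on randomization group, time and their interaction adjusted for random individual intercept". All three arms enter, no further covariates are allowed, and "The dose stable group will be set as the reference to which the dose escalation and placebo groups will be compared". Coding is left open: "Visit will be treated as a numeric variable if there is no plateau effect"; otherwise Visit is a factor. SAP 2.3.2 adds that "All calculated p-values will be two-sided and compared to a 5% significance level", without adjustment for multiplicity.

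No safeguard for the covariance is planned. SAP 5.1.4 checks only normality of ANCOVA residuals, and SAP 5.1.6 only compares FAS with PPS.

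On the response itself, Protocol 1.3.2 says of the earlier trial: "The magnitude of the cerebral NAD-increase showed high interindividual variation". It adds that three participants showed no cerebral response. SAP 1.1 says: "This response was heterogeneous, and it is unknown if this was due to inadequate dosing". For placebo, Protocol 10.1 says: "whereas the change in the placebo group was negligible at -0.43" per cent.

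**The concern.** A random intercept with one residual variance assumes the same variance at every visit in every arm, and the same correlation between any two visits. The design may break both. V1 is off drug. If each participant has a personal response to NR that lasts through V2–V4, change from V1 varies much more than change between on-drug visits, and placebo participants contribute none of this variation. The fitted residual averages the large and small components and is then applied to the change-from-baseline contrast.

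The analysis serves a named secondary objective, dose-response over weeks 4, 8 and 12 (SAP 1.3.2), and any p below 0.05 will be called significant. SAP 4.4 and 5.3 provisionally extend the same model to every exploratory endpoint measured at V1–V4.

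**Working it through.** **Inputs.** Arms DE 40, DS 20, PL 20 (Protocol 4.2); four visits; two-sided 5%. Earlier trial (Protocol 1.3.2, its Figure 1 legend, and 10.1): NR +27%, paired p = 0.016; placebo −0.43%, paired p = 0.75. Assumed: 15 per arm with spectroscopy, and percentages on the scale of the t-tests.

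**Starting point.** When the model's assumptions hold (equal responses, factor Visit), simulation gives 5.2–5.4%, so the nominal level is reproduced.

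**SD of change** = mean × √n / t, with 14 df.
- NR: 27% × √15 / 2.74 = 38%; variance 0.146.
- Placebo: 0.43% × √15 / 0.325 = 5.1%; variance 0.0026. Residual SD per scan σ = 5.1% / √2 = 3.6%; σ² = 0.0013.
- Variance of individual response: τ² = 0.146 − 0.0026 = 0.143.

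**DE–DS at week 12, factor Visit, V1 included, fully persistent response, no true difference.** A response pattern (0, b, b, b) has sum of squares 0.75b² about its mean on 3 df, so it adds τ²/4 to the residual. Three quarters of participants receive NR:
- residual = 0.75 × 0.143/4 + 0.0013 = 0.028
- model SE = √[2 × 0.028 × (1/40 + 1/20)] = 0.065
- true SE = √[0.146 × (1/40 + 1/20)] = 0.105
- ratio 0.62; rejection = 2 × [1 − Φ(1.96 × 0.62)] = 22%.

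Simulation agrees (22–23%). A Welch test on change gives 5.1%.

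**Partial persistence.** If a person's responses at two visits correlate at ρ, the response adds τ²(0.75 − 0.5ρ) instead of τ²/4.

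| ρ | SE ratio, DE–DS | Rejection | SE ratio, DS–PL |
|---|---|---|---|
| 1 | 0.62 | 22% | 0.87 |
| 0.75 | 0.76 | 14% | 1.06 |
| 0.5 | 0.87 | 9% | 1.22 |
| 0.25 | 0.97 | 6% | 1.36 |
| 0 | 1.06 | 4% | 1.49 |

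The DS–PL column uses model SE √[2 × residual × (1/20 + 1/20)] and true SE √[(0.146 + 0.0026)/20] = 0.086. That contrast is anti-conservative (about 9%) at ρ = 1 and conservative from ρ = 0.75 down.

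**More measurement noise**, holding the NR SD of change at 38% and ρ = 1: σ of 15, 20 and 25% gives about 14, 10 and 6%.

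**Numeric Visit.** With visits scored 0–3, a persistent response has slope 0.3b. True slope variance per person = 0.09 × 0.143 + 0.0013/5 = 0.0131; the model uses residual/5. With residual 0.028 the SE ratio is 0.65 and rejection 20%. If a 27% mean step misfitted by the straight line also enters the residual (0.75 × 0.30 × 0.27²/3 = 0.0055, total 0.034), the ratio is 0.72 and rejection 16%. At response-to-residual SD ratios of 0.5, 1, 1.5, 2 and 3, simulation gives 2, 3, 5, 7 and 12%.

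**V1 not an outcome row.** A constant response over V2–V4 is absorbed by the random intercept, and the simulated rate is 5%. If the spread of responses grows linearly over those visits, it is 22%.

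**Spread growing linearly, V1 included** (simulated): week 12 29%, slope 26%, week 4 0.3%. The documents give no figure on whether spread grows.

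**Which repairs work** (ρ = 1, factor Visit).
- Common unstructured covariance over three arms: pooled change variance 0.75 × 0.146 + 0.25 × 0.0026 = 0.110; SE ratio √(0.110/0.146) = 0.87; about 9%. A common random slope also simulates at about 9%.
- Dropping placebo but keeping the random intercept: residual 0.143/4 + 0.0013 = 0.037; ratio √(2 × 0.037/0.146) = 0.71; about 16%.
- Arm-specific variances: about 5%.

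**The case against.** A reader might infer that the standard errors are simply too small and that false positives run well above 5%. The documents do not support that without conditions. They give no SD, no within-person variance and no correlation across visits. Persistence is suggested by the MRS-responder definition in the Protocol's abbreviation list, which treats response as a trait, and by the plateau at 1–2 weeks stated in Protocol 10.3. It was not observed, because the earlier trial had one post-baseline scan.

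The 5% placebo SD is also fragile, since it comes from a near-zero mean. With the same p-value, a mean change of −1, −1.5 or −2% on the test's scale would imply an SD of 12, 18 or 24%. Fewer participants with spectroscopy in the earlier trial (10–13 per arm) would put the NR SD at 29–35%.

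The SAP does not settle whether V1 is an outcome row: it speaks of change from baseline but also of NAD at weeks 4, 8 and 12. Without a V1 row and with no added covariates, the model could not estimate change from baseline, so inclusion is the more natural reading, but it is not stated.

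A reader might also take this as a threat to the main result. It is not. The week-12 DE–DS comparison is tested by the ANCOVA in SAP 5.1.2, which uses DE and DS only and no visit covariance. Nor is DS–PL simply conservative; it can err either way. For exploratory endpoints, SAP 4.4 and 5.3 call the plan preliminary, and the cited heterogeneity concerns cerebral NAD.

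All of this stands and limits the size of the problem. It does not remove it: the level of the test depends on unknown quantities, the sponsor's own description of NR response points in the unfavourable direction, and nothing in the SAP would reveal or correct the error.

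**Conclusion.** The working covariance in SAP 5.1.7 is not robust to the individual variation in NR response that the documents themselves report. The size is conditional. With V1 as an outcome row, a fully persistent response and the SDs implied by the earlier trial, the DE–DS week-12 false-positive rate is about 22%. With larger measurement noise or partial persistence it is about 6–14%. If responses do not persist, or if only V2–V4 are modelled with a constant response, it is about 4–6%. The numeric slope ranges from conservative to about 16–20% under a constant response. These figures assume normal responses, complete data and equal DE and DS means. The matter is worth correcting before analysis, but it concerns a secondary analysis and, provisionally, the V1–V4 exploratory endpoints.

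**What to change.** Keep the mean model and change the basis of inference in SAP 5.1.7. Either of these would do:
- Subject-level cluster-robust (CR2) standard errors with small-sample degrees of freedom. With complete data and factor Visit this uses each arm's own variance of change, as the Welch test does. It is the simpler choice.
- Arm-specific covariance, for example a random intercept plus a random on-drug effect with arm-specific residual variance, or an unstructured visit covariance fitted to DE and DS without placebo. Protocol 10.4 describes this analysis for DE and DS only.

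A random slope alone, or one unstructured covariance over all three arms, is not enough. State whether V1 is an outcome row.

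The cost is SAP wording and a different R call. Some intervals will widen. A fully arm-specific unstructured covariance has 3 × 10 = 30 parameters, with only 20 people in each of DS and PL before drop-out, so name a simpler fallback for non-convergence.
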